6.1.1 Overview

This trial is a multi-centre, prospective trial, consisting of an initial open-label treatment phase of 4 weeks followed by a randomised, double-blind, vehicle-controlled, maintenance phase of 52 weeks in subjects with psoriasis vulgaris.

After the screening phase, subjects deemed eligible for the trial (adults with psoriasis vulgaris on the trunk and/or limbs rated as at least ‘mild’ according to the PGA, BSA 2-30% and m-PASI of at least 2) will be enrolled to the initial open-label phase, where they will apply LEO 90100 once daily on the psoriatic lesions on trunk and/or limbs for 4 weeks.

- Subjects who achieve treatment success (PGA score of ‘clear’ or ‘almost clear’ with at least a 2-grade improvement from baseline) at Week 4 will be randomised in a 1:1 ratio to a maintenance phase of 52 weeks with LEO 90100 or vehicle (maintenance IP) twice weekly.
- Subjects who do not achieve treatment success after 4 weeks of once daily treatment (i.e., non-responders) will be discontinued from the trial.

During the randomised maintenance phase, subjects will apply maintenance IP twice weekly 3 or 4 days apart (fixed days) on all areas on the trunk and limbs where lesions have cleared or almost cleared after the initial open-label phase or after relapse treatment. Subjects will be assessed regularly at clinical visits (every 4 weeks). In addition, if in the opinion of the

subject, a relapse (exacerbation of psoriasis) has occurred between two regular monthly visits, the subject will be assessed by the investigator at an unscheduled visit.

Following confirmation of a relapse the subject will be provided with rescue IP and will be asked to apply it to the active area(s) on trunk and/or limbs, irrespective of whether those areas were active at baseline or they are new lesions. The rescue IP is to be applied once daily on the active areas for 4 weeks. (Note: This treatment is referred to as 'relapse' or 'rescue' treatment). If additional areas become active during rescue treatment, these should also be treated once daily with rescue IP. During a relapse, areas that are not active will continue twice weekly maintenance treatment.

- If a score of 'clear'/'almost clear' according to the PGA is regained after 4 weeks, the twice weekly maintenance regimen will be re-started on the now 'clear'/'almost clear' area(s) according to the original randomisation scheme (for details see section [6.1.4](#)).

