- Subjects who do not use rescue medication at Visit 15 will have a final contact (FU3) 8 weeks after Visit 15. Relapses confirmed at Visit 15 will be treated at the investigator's discretion; treatment with Enstilar[®] or IP is not allowed.
- Subjects who have completed 4 weeks of rescue treatment at Visit 15 (that is, Visit 15 is a relapse follow-up visit, see section 6.1.4.1) will have a final contact (FU3) 8 weeks after Visit 15.
- For subjects who use rescue medication at Visit 15 (that is, rescue medication was dispensed at an unscheduled visit after Visit 14 [see section 6.1.4.2]), the 8-week follow-up period will start after completion of the 4-week rescue treatment regimen (that is, at the relapse follow-up visit).

- Subjects who withdraw early from the trial, including subjects who leave the trial after the initial 4 weeks open-label treatment, will also have a follow-up visit (FU3) 8 weeks after their last IP application.

Subjects who experience rebound during the follow-up period prior to the FU3 visit will contact the site as soon as possible for an unscheduled follow-up visit (see below).

If the subject has not experienced a worsening of their psoriasis during the 8-week follow-up period, the FU3 contact may be conducted as a telephone contact, at the discretion of the investigator. If rebound is confirmed at the FU3 visit, the subject will be followed up for 14 days or until resolution (whichever occurs first). If the rebound is considered an SAE, the event must be followed up until a final outcome has been established, i.e. the follow-up may continue beyond the end of the clinical trial (see section [9.5](#)).

Rebound events in the follow-up period will be reported as (S)AEs in accordance with sections [9.2](#) and [9.4.1](#). See section [9.5](#) for the follow-up of related AEs during and after the trial.

Unscheduled follow-up visit

At the last treatment visit (Visit 15/Early Withdrawal), subjects should be instructed to contact the site if they experience a worsening of their psoriasis within the following 8 weeks to schedule a follow-up visit ('unscheduled follow-up'). The unscheduled follow-up visit should take place no more than 7 days after the initial contact.

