11.3.6.2 Rebound

Rebound will be defined as (i) an m-PASI ≥ 12 AND an increase in m-PASI of $\geq 125\%$ of the baseline value, or (ii) new pustular, erythrodermic or more inflammatory psoriasis either a) within 2 months after discontinuation of once-daily treatment in the initial open-label phase, b) within 2 months after discontinuation of once-daily relapse treatment, or c) within 2 months after end of maintenance treatment (up to Visit FU3)

Number of rebounds within two months after entering the maintenance phase will be summarised by treatment group in a table.

Number of rebounds occurring after the first two months of maintenance treatment (i.e. including the follow-up period) will be summarised by treatment group in another table.

Subjects with m-PASI $\geq 125\%$ of baseline (Visit1) score and cases of rebound will be listed.

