5.2 Trial Analysis Sets

The trial analysis sets are defined in [Table 2](#). The analysis sets are described in more detail in the Analysis Set Definition Document.

Table 2: Trial analysis sets

Analysis set	Definition
Enrolled subjects	All subjects enrolled (informed consent obtained) in the trial.
Open-label safety analysis set	All subjects exposed to LEO 90100 during the open-label phase.
Open-label HPA analysis set	All subjects in the open-label safety analysis set who provided consent for the Adrenocorticotrophic Hormone (ACTH) challenge test and underwent a Hypothalamic-Pituitary-Adrenal (HPA) axis test.
Full analysis set	All subjects randomised who had treatment success at randomisation, defined as PGA score of 'clear' or 'almost clear' with at least a 2-grade improvement from baseline. Subjects randomised without treatment success will be excluded from the full analysis set. This approach is in alignment with the ICH E9, since achieving treatment success is a major randomisation criterion measured prior to randomisation and therefore exclusion of such subjects will not introduce bias.
Per protocol analysis set	The per protocol analysis set will be defined by excluding subjects from the full analysis set as described in the protocol and in the Analysis Set Definition Document.
Safety analysis	All subjects exposed to IMPs following randomisation and with available

set	post-randomisation safety evaluations.
Randomised subjects	All subjects randomised to the maintenance phase.
HPA analysis set	All subjects in the safety analysis set who provided consent for the ACTH challenge test and underwent an HPA axis test.

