5.5.4 Rebound

Rebounds will be defined as described in the protocol. The baseline value will be the m-PASI value measured at the start of the rebound follow-up period. A rebound follow-up period is defined as either (i) 2 months after discontinuation of open-label phase treatment, (ii) 2 months after discontinuation of relapse treatment, or (iii) 2 months after discontinuation of maintenance treatment (up to Visit FU3).

Number of rebounds occurring within the first 2 months after discontinuation of the open-label phase treatment, and number of rebounds occurring within 2 months after discontinuation of relapse treatment will be summarised by treatment group.

Number of rebounds occurring within two months after discontinuation of maintenance treatment will be summarised by treatment group.

Cases of rebounds will be listed.

More details for the tables and listings can be found in [Appendix I](#) and [Appendix II](#).

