Table 3-66 Frequent adverse events ($\geq 1\%$ in any treatment group) during the first 28 weeks of the randomised phase by SOC, preferred term, and randomised treatment: safety analysis set

Table 3-67 Frequent adverse events ($\geq 1\%$ in any treatment group) during the last 32 weeks of the randomised phase by SOC, preferred term, and randomised treatment: safety analysis set

Table 3-68 Frequent adverse events ($\geq 1\%$ in any treatment group) during the total maintenance phase by SOC, preferred term, randomised treatment, and rescue medication: safety analysis set

Table 3-69 Frequent adverse events ($\geq 1\%$ in any treatment group) during the first 28 weeks of the maintenance phase by SOC, preferred term, randomised treatment, and rescue medication: safety analysis set

Table 3-70 Frequent adverse events ($\geq 1\%$ in any treatment group) during the last 24 weeks of the maintenance phase by SOC, preferred term, randomised treatment, and rescue medication: safety analysis set

Table 3-71 Summary of rebounds occurring within 2 months after discontinuing open-label phase treatment or relapse treatment: safety analysis set

Table 3-72 Summary of rebounds occurring within 2 months after discontinuation of maintenance treatment : safety analysis set

Table 3-73 Physician's assessment of local safety and tolerability by visit in open-label phase: open-label safety analysis set

Table 3-74 Shift table for physician's assessment of local safety and tolerability from start to end of open-label phase: open-label safety analysis set

Table 3-75 Physician's assessment of local safety and tolerability by visit not related to relapse: safety analysis set

Table 3-76 Physician's assessment of local safety and tolerability by visit for start of relapse: safety analysis set

Trial ID: LP0053-1004	Date: 15-JUL-2019	Version: 1.0 Page 60 of 177
------------------------------	--------------------------	--------------------------------

Table 3-77 Physician's assessment of local safety and tolerability by visit for end of relapse: safety analysis set

Table 3-78 Shift table for physician's assessment of local safety and tolerability from start of relapse to end of relapse by visit for start of relapse: safety analysis set

Table 3-79 Subject's assessment of local safety and tolerability by visit in open-label phase: open-label safety analysis set

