Mean (SD)	xx.x (xx.x)	xx.x (xx.x)	xx.x (xx.x)
Median	xx.x	xx.x	xx.x
Q1;Q3	xx.x;xx.x	xx.x;xx.x	xx.x;xx.x
Min;Max	xx.x;xx.x	xx.x;xx.x	xx.x;xx.x

Shell 101: Summary of rebounds occurring within 2 months after discontinuing open-label phase treatment or relapse treatment: safety analysis set

	LEO 90100 (n=xxx)	Vehicle (n=xxx)
Within 2 months after discontinuation of open-label treatment:		
Number of rebounds	xxx	xxx
Number of subjects	xxx	xxx
Mean (SD)	xx.x (xx.x)	xx.x (xx.x)
Median	xx.x	xx.x
Q1;Q3	xx.x;xx.x	xx.x;xx.x
Min;Max	xx.x;xx.x	xx.x;xx.x
Within 2 months after discontinuation of relapse treatment:		
Number of rebounds	xxx	xxx
Number of subjects	xxx	xxx
Mean (SD)	xx.x (xx.x)	xx.x (xx.x)
Median	xx.x	xx.x
Q1;Q3	xx.x;xx.x	xx.x;xx.x
Min;Max	xx.x;xx.x	xx.x;xx.x

Shell 102: Summary of rebounds occurring within 2 months after discontinuing of maintenance treatment: safety analysis set

	LEO 90100 (n=xxx)	Vehicle (n=xxx)
Within 2 months after discontinuation of maintenance treatment:		
Number of rebounds	xxx	xxx
Number of subjects	xxx	xxx
Mean (SD)	xx.x (xx.x)	xx.x (xx.x)
Median	xx.x	xx.x
Q1;Q3	xx.x;xx.x	xx.x;xx.x
Min;Max	xx.x;xx.x	xx.x;xx.x

Signature Page for TMF-000023733 v1.0

Reason for signing: Approved	Manage Name: PPD Capacit Date of signature: 15-Jul-2019 08:57:51 GMT+0000	(s)
Reason for signing: Approved	Manage Name: PPD Capacit Date of signature: 15-Jul-2019 09:16:48 GMT+0000	dict(s)
Reason for signing: Approved	QC App Name: PPD Capacit Date of signature: 15-Jul-2019 09:20:55 GMT+0000	

Electronic signatures made within eTMF LEO are considered to be a
legally binding equivalent of traditional handwritten signatures.

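### Rebound after stopping open-label treatment is tabulated only for randomised subjects, so Week 4 leavers followed for rebound have no count or denominator

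*SAP*

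**What the plan says.** Protocol 5.3 names incidence of rebound among the safety assessments. The definition in protocol 11.3.6.2 includes as its first window events "within 2 months after discontinuation of once-daily treatment in the initial open-label phase".

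Protocol 6.1.1 states: "Subjects who do not achieve treatment success after 4 weeks of once daily treatment (i.e., non-responders) will be discontinued from the trial". Protocol 6.1.5 asks for rebound follow-up of all subjects for 8 weeks after the last application, and extends this to early leavers, "including subjects who leave the trial after the initial 4 weeks open-label treatment, will also have a follow-up visit (FU3") 8 weeks after their last dose.

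On reporting, protocol 11.3.6.2 plans a count by treatment group for the first two months of the maintenance phase, a second table for later rebounds, and a listing of cases. SAP 5.5.4 plans to summarise by treatment group the "Number of rebounds occurring within the first 2 months after discontinuation of the open-label phase treatment", and to list cases. Table 3-71 in SAP Appendix I is "Summary of rebounds occurring within 2 months after discontinuing open-label phase treatment or relapse treatment: safety analysis set"; its layout, Shell 101 in Appendix II, carries the same title. SAP 5.2 defines that set as "All subjects exposed to IMPs following randomisation and with available" post-randomisation safety data. The same section also defines an open-label safety analysis set: "All subjects exposed to LEO 90100 during the open-label phase".

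**The concern.** The protocol sets up a rebound window for stopping once-daily treatment and follows the subjects who stop at Week 4 through that window. The summary table then uses a population that none of those subjects can enter. A named safety measure is thus reported without one of the groups followed for it.

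The omission is selective. Randomisation requires treatment success, so apart from anyone randomised in error the tabulated subjects are responders. They also go on to a trial product: LEO 90100 twice weekly or foam vehicle. Subjects who did not respond and whose treatment ended altogether are left out. A reader of Table 3-71 could take its figures as the incidence of rebound after a 4-week course, when they describe responders who continued in the trial.

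**Working it through.** **1. Who can enter the table.**
- Open-label safety analysis set: exposed to LEO 90100 in the open-label phase, randomised or not.
- Safety analysis set: exposed after randomisation. A Week 4 leaver fails this condition.
- Tables 3-71 and 3-72, the only rebound tables, both use the safety analysis set. Shell 101 has two columns, LEO 90100 and Vehicle.

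**2. Whether another table captures these cases.**
- Rebound must be reported as an adverse event (protocol 9.1 and 9.3.6), so the open-label adverse event tables are the natural candidate. The footnotes to Shells 59, 62 and 65 limit them to events during exposure time in the open-label phase. Rebound after stopping falls outside that.
- SAP Table 1 starts the follow-up phase after the last maintenance or rescue product, which leavers never receive. It ends the open-label phase on the day before randomisation, which leavers never reach. No defined period clearly covers their 8 weeks.
- What remains is Listing 7-9 (rebounds) and Listing 7-5 (adverse events).

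**3. Planned size of the omitted group.** Inputs from protocol 11.1: 48% success at Week 4; 832 included to give 90% probability of at least 380 randomised.
- Reproducing the 832: for X ~ Binomial(832, 0.48), P(X ≥ 380) = 0.916. The smallest n reaching 0.90 is 830 (probability 0.905). The plan's figure reproduces.
- Expected randomised: 0.48 × 832 = 399.
- Expected not randomised: 0.52 × 832 = 433, or 52%.
- If exactly 380 were randomised: 832 − 380 = 452, or 452/832 = 54%. This is the target count, not the expectation, so 52% is the figure to use.

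**4. What is known of the actual size.** SAP Table 8 gives 132 + 55 + 52 + 68 + 56 + 68 + 114 = 545 randomised. The number treated is not given, so the share depends on the success rate assumed:

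| Success rate | Treated (545 / rate) | Not randomised | Share |
|---|---|---|---|
| 48% (protocol) | 1135 | 590 | 52% |
| 70% (assumed) | 779 | 234 | 30% |
| 80% (assumed) | 681 | 136 | 20% |

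Across this range the omitted group is at least a fifth of those treated.

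**The case against.** There is a fair case on the other side.

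- **The SAP follows the protocol.** Protocol 11.3.6.2 already counts early rebounds from entry to the maintenance phase and by treatment group. This stands: the SAP carries the restriction forward. It does not make the restriction suitable for a window defined by stopping open-label treatment.
- **Withdrawal of active drug is tabulated.** Vehicle has no active ingredient, so vehicle subjects also stop calcipotriol/betamethasone at Week 4. They have scheduled m-PASI assessments every 4 weeks and a randomised comparator. A reader might infer that the plan gives no estimate of rebound after withdrawing active drug; that would be wrong. The estimate exists, in responders who continue on foam vehicle.
- **The adverse event tables may pick the cases up.** Protocol 11.3.6.1 sets no end to the treatment-emergent period, and SAP 5.5.3 assigns events by onset date. The shell footnotes are also not fully reliable: the one on Shell 60 names the maintenance phase although that shell also serves randomised-phase tables. This makes the route ambiguous; it does not assure a rebound count.
- **The data may be partial.** A reader might infer that every leaver has 8 weeks of follow-up data. Amendment 3 (December 2016) described the 8-week follow-up for the end of, or withdrawal during, maintenance. Follow-up of open-label leavers was made explicit only in Amendment 6 (April 2018), while enrolment was planned from Q1-2017. FU3 may also be a telephone contact when there was no worsening, and m-PASI is then not required. This stands and shapes the fix.
- **A rate in this group is hard to interpret.** Leavers may start follow-up with uncleared disease, and other therapy may be used. This argues for a caveat, not for having no count.

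**Conclusion.** The concern holds as a gap in safety reporting. Subjects who leave at Week 4 without randomisation are to be followed for rebound, but nothing in the plan assures a count or denominator for them. They are about 52% of those treated under the protocol's 48% success assumption. The actual share cannot be read from the documents; 20% to 30% would apply if success were 80% to 70%.

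Two stronger readings should be resisted. The first is that the cases are lost: they are to be listed. The second is a precision claim, such as an upper bound of about 0.7% from zero events in 433. That bound is one-sided, uses the planning number, and treats every leaver as assessed, none of which the documents support.

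No efficacy analysis or test is affected. The consequence is that the tabulated incidence describes responders only and leaves out the one group that stops all trial product.

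**What to change.** Split Table 3-71 and Shell 101. Keep the relapse-treatment part on the safety analysis set. Produce the open-label part on the open-label safety analysis set, with columns for LEO 90100, vehicle and 'Not randomised'. For the added column, report:

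- subjects with rebound, over subjects with an FU3 or unscheduled follow-up contact;
- how many of those had an on-site m-PASI;
- how many had no follow-up, showing separately those who left before Amendment 6.

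Present it descriptively, without a test or a confidence bound. Add a footnote that ascertainment is incomplete (telephone FU3, other therapy allowed in follow-up) and that the column is not comparable with the randomised arms. Record the change in SAP 5.7, since it departs from protocol 11.3.6.2.

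The cost is small: one column and a footnote, with no new data collection. Shells 30, 36 and 68 already separate randomised from not randomised subjects on this analysis set, so the layout exists. The real downside is that an incompletely ascertained figure will sit beside better-observed ones, which is why the number assessed must be shown with it.

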Appendix 2.1: Discontinued Subjects

Listing 1-1. Screening Failures

Listing 1-2. Reasons for Withdrawal from Trial in the Open-Label Phase

Listing 1-3. Reasons for Withdrawal from Trial in the Maintenance Phase

Listing 1-4. Subjects not entering the maintenance phase

Appendix 2.2: Protocol Deviations

Listing 2-1. Protocol Deviations

Listing 2-2. Comments from CRF

Trial ID: LP0053-1004	Date: 15-JUL-2019	Version: 1.0 Page 63 of 177
------------------------------	--------------------------	--------------------------------

Appendix 2.3: Trial Analysis Sets

Listing 3-1. Trial Analysis Set

Listing 3-2. Reasons for Exclusion from Analysis Set

Appendix 2.4: Demographic Data

Listing 4-1. Demographics

Listing 4-2. Date/Age of First Diagnosis of Psoriasis

Listing 4-3. Actual Trial Period

Listing 4-4. Medical History

Listing 4-5. Concurrent Diagnoses at Baseline

Listing 4-6. Concomitant Medication

Listing 4-7. Concurrent Procedures

Listing 4-8. Previous Anti-Psoriatic Treatment

Listing 4-9. Location of Psoriasis

Listing 4-10. Location of other Psoriasis

Appendix 2.5: Compliance and/or Investigational Product Concentration Data

Listing 5-1. Administration of Investigational Product

Listing 5-2. Drug Accountability

Trial ID: LP0053-1004	Date: 15-JUL-2019	Version: 1.0 Page 64 of 177
------------------------------	--------------------------	--------------------------------

Appendix 2.6: Efficacy Data

Listing 6-1. Dermatology Quality Life Index

Listing 6-2. EQ-5D-5L-PSO

Listing 6-3. Work Productivity and Activity Impairment: Psoriasis (WPAI:PSO)

Listing 6-4. Psoriasis Symptom Inventory (PSI)

Listing 6-5. Physician's Global Assessment of Disease Severity (PGA)

Listing 6-6. Physician's Assessment of the Extent and Severity of Clinical Signs (m-PASI)

Listing 6-7. Investigator's Assessment of Body Surface Area (BSA)

Listing 6-8. Subject's Global Assessment of Disease Severity (SGA)

Listing 6-9. Target Lesion/Location Score

Listing 6-10. Number of Active Treatment Days during the Maintenance Phase

Listing 6-11. Time to First Relapse

Listing 6-12. Proportion of Days in Remission

Listing 6-13. Number of Relapses

Appendix 2.7: Safety Data

Listing 7-1. Deaths

Listing 7-2. Serious Adverse Events

Listing 7-3. Subjects withdrawn from trial due to Adverse Events

Listing 7-4. Severe Adverse Events

Listing 7-5. Adverse Events

Trial ID: LP0053-1004	Date: 15-JUL-2019	Version: 1.0 Page 65 of 177
------------------------------	--------------------------	--------------------------------

Listing 7-6. Adverse Events Associated with Long Term Corticosteroid Use

Listing 7-7. Subjects Assessment of Local Safety and Tolerability

Listing 7-8. Investigators Assessment of Local Safety and Tolerability

Listing 7-9. Rebounds

Appendix 2.8: Listing of Laboratory Values by Subject

Listing 8-1. Physical Examination, Abnormal Findings

Listing 8-2. Laboratory Measurements

Listing 8-3. Abnormal Laboratory Measurements

Listing 8-4. Clinically Significant Laboratory Measurements

Listing 8-5. Vital Signs

Listing 8-6. Clinically Significant Vital Signs

Listing 8-7. ACTH Laboratory Measurements

Trial ID: LP0053-1004	Date: 15-JUL-2019	Version: 1.0 Page 66 of 177
------------------------------	--------------------------	--------------------------------

Additional Tables for Results Reporting in Clinical Trial Data Registries

Table 4-1 Non-serious AEs occurring in $\geq 1\%$ subjects by MedDRA primary SOC and preferred term: open-label safety analysis set

Table 4-2 Non-serious AEs occurring in $\geq 1\%$ subjects by MedDRA primary SOC and preferred term: safety analysis set

Table 4-3 Serious AEs by MedDRA primary SOC and preferred term: open-label safety analysis set

Table 4-4 Serious AEs by MedDRA primary SOC and preferred term: safety analysis set

Table 4-5 Subject enrolment and treatment assigned: enrolled subjects and subjects assigned treatment

Trial ID: **LP0053-1004**

Date: **15-JUL-2019**

Version: 1.0

Page 67 of 177

